11.3 Statistical Analysis Plan

The primary outcome is the change in whole blood NAD+ levels from baseline to day 6 compared between $RiaGev^{TM}$ and comparator.

An effectiveness analysis based on the intent-to-treat population and an efficacy analysis based on the per protocol population will be performed. Safety analysis will be done for the safety population.

Variables will be tested for normality and transformed to the log scale if found to be non-normally distributed. Log-normally distributed variables will be analyzed in the logarithmic domain. Intractably non-normal outcome variables will be analyzed by appropriate non-parametric tests.

Missing values in the intent-to-treat and per protocol analyses will be imputed using the most recent previously-available value (LOCF, or "last-observation-carried-forward" imputation) or multiple imputation methods. No imputation will be performed for missing safety values.

For each continuous endpoint, a summary table will be prepared with a variety of summary statistics including mean, standard deviation, median and range values for each time point-treatment pairing. To account for any a priori differences between groups, the summary statistics of the changes from baseline will also be provided. For parameters requiring a logarithmic transformation, the summary statistics will be provided as non-transformed values. Mean values will be displayed as graphs, with a separate line for each product, and error bars indicating standard errors or standard deviations. Mean changes from baseline will be graphed similarly. Although imputed data will be used for significance testing, non-imputed data will be used for presenting summaries. Categorical variables will be summarized as counts and percentages.

Continuous efficacy endpoints will be tested for significance between groups by Analysis of Covariance (ANCOVA). The dependent variable will be the measurement at each visit, the factor will be the treatment group, and the value at baseline (Day 1) will be the covariate. A within group analysis on effectiveness/efficacy endpoints will be done using the Student's paired t-test or, in the case of intractable non-normality, the Wilcoxon sign rank test. Categorical variables will be compared using Chi-squared or Fisher's Exact tests as appropriate.

Probabilities < 0.05 will be considered statistically significant. All statistical analysis will be completed using the R Statistical Software Package Version 3.5.2 (R Core Team, 2018) for Microsoft Windows.

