6 STUDY DESIGN

This will be a randomized, double-blind, comparator-controlled, crossover, safety and efficacy study conducted at Prism Clinical Research Clinic, Saint Paul, MN, USA, a KGK Science Inc. partner.

The planned sample size for this study is 18, crossing over once is equivalent to 36 participants. To evaluate the outcomes, study assessments will be conducted as per the schedule of assessments in section 1.3

Study Arm	Number of Participants
RiaGev [™] → Comparator	N = 9
Comparator→ RiaGev [™]	N = 9
Total	N = 18

investigate the safety and efficacy of RiaGev[™] in healthy adults

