11 STATISTICAL EVALUATION

11.1 Determination of Sample Size

The planned total sample size will be 18 with 9 participants randomized to each treatment schedule. This sample size will enable detection of a difference of 8.7 pMol/mg protein in NAD+ concentration between the two treatments at an overall 5% significance level and 80% power. This sample size takes into account a loss to follow up rate of 20%.

This calculation is based on a critical difference in NAD+ concentration, between NR and placebo of 6.1 pMol/mg protein and a standard deviation of 11.04 units reported in a study by Martens et al. (2018)(13).

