2.2 Effectiveness/Efficacy analysis

2.2.1 Primary Outcome:

The primary outcome is the change in whole blood NAD⁺ levels from baseline to day 8 when supplemented with RiaGev™ or comparator.

The primary null hypothesis is as follows:

H₀: There is no significant difference in mean change in NAD⁺ level from pre-supplementation to post-supplementation, between subjects taking RiaGev™ or comparator.

Possible differences before exercise from day 1 to days 3, 5 and 8 between the study groups will be assessed using repeated-measures mixed ANCOVA. The model will include treatment, visit number, sequence and period as fixed effects and subject as a random effect. Between group p-values will be obtained from this model, while within group p-values will be obtained using paired t tests or Wilcoxon Signed Rank test as appropriate.

Possible differences at after exercise from day 1 to day 8 between the study groups will be assessed using repeated-measures mixed ANCOVA. The model will include treatment, visit number, sequence and period as fixed effects and subject as a random effect. Between group p-values will be obtained from this model, while within group p-values will be obtained using paired t tests or Wilcoxon Signed Rank test as appropriate.

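### Protocol 11.3 tests primary NAD+ with an ANCOVA that ignores the crossover pairing, SAP 2.2.1 names a different primary test, and neither document says which governs

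*Protocol*

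**What the plan says.** Protocol 11.1 randomises to sequences: "The planned total sample size will be 18 with 9 participants randomized to each treatment schedule". Under Protocol sections 9.3 to 9.11 every participant has NAD+ measured on Days 1, 3, 5 and 8 of both periods.

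For the comparison between products, Protocol 11.3 specifies an ANCOVA: "The dependent variable will be the measurement at each visit, the factor will be the treatment group". The Day 1 value is the covariate, and no subject, period or sequence term is listed. Paired tests appear in that section only for within-group change.

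Protocol section 6 says that "crossing over once is equivalent to 36 participants".

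On power, Protocol 11.1 states: "This sample size will enable detection of a difference of 8.7 pMol/mg protein in NAD+ concentration between the two treatments". The power claimed for that difference is 80% with a 5% test, after allowing for 20% loss. The stated input is "a standard deviation of 11.04 units", without saying whether this is a per-period SD or the SD of a within-person difference.

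SAP 2.2.1 gives a repeated-measures mixed ANCOVA for the same outcome: "The model will include treatment, visit number, sequence and period as fixed effects and subject as a random effect". Its Table 3 repeats the method. Although the model is called an ANCOVA, the Day 1 value is not among the listed terms.

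**The concern.** The treatment contrast in this design is within-person. An ordinary ANCOVA treats a participant's two Day 8 values as if they came from two people. Any person-level variation that the Day 1 covariate does not remove stays in the error term, although it cancels from the estimate. The printed standard error is then too large, the test runs below its nominal 5%, and power may fall short of the 80% in Protocol 11.1. The count of 36 in Protocol section 6 follows the same logic, which holds only if a person's two periods are uncorrelated.

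The second problem is that two prespecified primary tests exist. They will in general give different p-values, and a reader cannot tell which was meant to decide the trial.

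**Working it through.** **Inputs.** From Protocol 11.1: difference 8.7, SD 11.04, N = 18, 20% loss (18 × 0.8 = 14.4 completers), 5% level, 80% power. Protocol 11.3 says only "Probabilities < 0.05 will be considered statistically significant", so two-sided testing is assumed. No within-person correlation is given in either document.

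**Step 1: the plan's own figure.** Read 11.04 as the SD of the within-person difference and use a paired t-test with noncentrality 8.7/(11.04/√n):

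- n = 14: 8.7/2.951 = 2.95, power 77.8%
- n = 15: 8.7/2.851 = 3.05, power 81.0%
- n = 18: 8.7/2.602 = 3.34, power 88.3%

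The stated 80% is therefore matched at 14 to 15 pairs. An unadjusted independent two-sample t-test, with 11.04 as the per-period SD and noncentrality 8.7/(11.04√(2/n)), gives:

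- n = 14 per product: 8.7/4.173 = 2.08, power 51.9%
- n = 18 per product: 8.7/3.680 = 2.36, power 63.2%

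**Step 2: what the Day 1 covariate does.** Let r_s be the correlation of Day 1 with Day 8 in the same period, and r_c the correlation of any two values from different periods. Fix the SD of the Day 8 within-person difference at 11.04, so σ² = 11.04²/[2(1 − r_c)].

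- Error variance that the ANCOVA attaches to the treatment contrast (same-period covariate): 2σ²(1 − r_s²)/n
- Variance of the paired contrast: 11.04²/n
- Ratio of the two: (1 − r_s²)/(1 − r_c)

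The ANCOVA loses against the paired test only where this ratio exceeds 1, that is where r_s² is less than r_c. If all correlations equal ρ, the ratio is 1 + ρ.

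**Step 3: simulated power at 14 completers, difference 8.7.** The equal-correlation rows from 0.3 to 0.8 use 3,000 runs each (Monte Carlo standard error about 0.9 points).

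| r_s | r_c | Ratio | ANCOVA, same-period Day 1 | ANCOVA, Visit 2 value in both periods |
|---|---|---|---|---|
| 0.3 | 0.3 | 1.30 | 70.5% | 72.2% |
| 0.5 | 0.5 | 1.50 | 63.1% | 65.0% |
| 0.7 | 0.7 | 1.70 | 58.2% | 62.0% |
| 0.8 | 0.8 | 1.80 | 55.8% | 58.1% |
| 0 | 0 | 1.00 | about 80% | – |
| 0.7 | 0.5 | 1.02 | about 80% | – |
| 0.6 | 0.3 | 0.91 | about 84% | – |
| 0.8 | 0.5 | 0.72 | about 92% | – |

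Separate runs of the 0.5/0.5 case gave between 63% and 69%. A within-person test with a period term has about 77% to 78% in every row. With the baseline difference also fitted it has about 72% to 74% in the equal-correlation rows. With all 18 completing and ρ = 0.5, the ANCOVA has 77% to 80% against about 88%.

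**Step 4: type I error.** At ρ = 0.5 the ANCOVA rejects a true null in 3.5% of runs (same-period Day 1) or 1.8% (Visit 2 value). The within-person tests reject in 5.0% and 4.9%. Across the cases examined the ANCOVA ranges from about 1% to 5%.

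**Step 5: why the replacement must keep Day 1.** If change from baseline were analysed in a crossover model without the Day 1 covariate, then under equal correlation the two changes have covariance ρ − ρ − ρ + ρ = 0 (in units of σ²). The SD of their difference is √2 × 11.04 = 15.61. The noncentrality at n = 14 is 8.7/(15.61/√14) = 2.09, and power is about 48%.

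**The case against.** The strongest reply is that the SAP already handles this. Its model has subject, period and sequence terms. It also looks like the later document: it describes enrolment in the past tense and cites R 3.6.1 where Protocol 11.3 cites 3.5.2. This stands in part. Any loss arises only if an analyst follows Protocol 11.3. But the available text does not say that the SAP replaces the protocol's test, so the conflict remains.

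A reader might infer that power simply drops from 80% to about 65%. The documents do not support that. The figure needs equal correlations near 0.5, and the loss disappears or reverses in the lower rows of the table. Setting it beside 80% is also not like for like, because the within-person test itself has about 77% at 14 completers.

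A reader might also infer that only a paired calculation can give 80%. Protocol 11.1 names no formula. A baseline-adjusted two-sample calculation reaches 80% with a baseline correlation of about 0.58 at 18 per product, or 0.67 to 0.70 at 15 or 14. The paired reading is the simplest match, not the only possible one.

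Finally, the error is on the cautious side. It risks a missed effect and does not inflate false positives.

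**Conclusion.** The point holds as a mismatch between the protocol's test and the design, and as an unresolved conflict between Protocol 11.3 and SAP 2.2.1. Under Protocol 11.3 the standard error would be mis-stated and the test generally conservative.

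The effect on power must be given as a range: from a loss of roughly 5 to 22 points (77% less 72%, 77% less 55%) under equal correlations of 0.3 to 0.8, to little or no loss when same-period correlation clearly exceeds cross-period correlation or correlation is near zero. This assumes 14 completers, a two-sided 5% test, 11.04 as the SD of the within-person difference, and, for the cases of no loss with unequal correlations, the same-period Day 1 value as covariate. The correction should be made, but the flaw is not fatal, because the SAP already contains most of the right model.

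**What to change.** - **Protocol 11.3:** replace the ANCOVA sentence with the SAP's crossover structure. For the primary contrast, use Day 8 NAD+ as the dependent variable; treatment, period and sequence as fixed effects; subject as a random effect; and the Day 1 value of the same period as a covariate.
- **SAP 2.2.1:** list that Day 1 covariate, and state that this model is the single primary test. If the protocol is not amended, a sentence in the SAP saying that it supersedes Protocol 11.3 would suffice.
- **Protocol section 6:** replace the equivalence to 36 with 18 within-person comparisons, about 14 after the 20% loss.

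The cost is wording. A protocol amendment may need IRB review under Protocol 9.16, while the SAP sentence alone avoids changing the protocol. The model has somewhat fewer error degrees of freedom than the ordinary ANCOVA. No new participants, samples or visits are needed.

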11.3.1 Premature Discontinuation Description

For each premature discontinuation, the following parameters will be listed: participant number, dates of start and end of treatment, and the reason of premature discontinuation.

11.3.2 Safety

For adverse events, a descriptive analysis will be given. Adverse events will be presented in a frequency table by category and treatment. Furthermore, description, frequency, severity and causality will be reported for each adverse event.

Continuous safety parameters (e.g. hematology, clinical chemistry, heart rate and blood pressure) will be summarized using a table including mean, standard deviation, median, minimum value, and maximum value for each measurement point. The changes from baseline will also be summarized similarly.

11.4 Protocol Deviation Description

Protocol deviations will be listed in the final study report.

11.5 Protocol Amendments

Once the protocol has been approved by the IRB, any changes to the protocol must be documented in the form of an amendment. All amendments will be documented in the final study report.

12 DATA COLLECTION AND STORAGE

All data collection and record storage will be done in compliance with ICH GCP Guidelines and applicable local regulatory guidelines. Existing, modified, and newly developed eCRFs (electronic case report forms) and clearly defined instructions for their correct use will be used to gather the study data. Quality assurance will be conducted on the database prior to collecting the data (anticipating problems with data collection), and quality control activities (such as recognition, monitoring and troubleshooting) will be conducted during and after the data is collected to ensure the integrity and validity of study results. The data will be handled and stored in OpenClinica Enterprise Version 4 (a cloud-based electronic case report form compliant with the industry regulations) and MS Access database.

13 ETHICAL ASPECTS OF THE STUDY

This study will be conducted with the highest respect for the individual participants (i.e., participants) according to the protocol, the ethical principles that have their origin in the Declaration of Helsinki, and the ICH Harmonised Tripartite Guideline for GCP.

13.1 IRB Approval

Prism Clinical Research and KGK Science Inc. will supply relevant documents for submission to an IRB for the protocol's review and approval. The following must be submitted to the IRB: this protocol, a copy of the informed consent form, and, if applicable, volunteer recruitment materials and/or advertisements and other documents required by all applicable laws and regulations. The IRB's written approval of the protocol and volunteer informed consent must be obtained before commencement of the study. The IRB approval must refer to the study by exact protocol title, number, and version date; identify versions of other documents (e.g., informed consent form) reviewed; and state the approval date.

Prism Clinical Research and KGK must adhere to all requirements stipulated by the IRB. This may include notification to the IRB regarding protocol amendments, updates to the informed consent form, recruitment materials intended for viewing by volunteers, local safety reporting requirements and submission of the investigator's annual/final status report to the IRB.

13.2 Volunteer Information and Informed Consent

Written consent documents will embody the elements of informed consent as described in the declaration of Helsinki and the ICH Guidelines for GCP and will be in accordance with all applicable laws and regulations. The informed consent form describes the planned and permitted uses, transfers, and disclosures of the volunteer's personal and personal health information for purposes of conducting the study. The informed consent form further explains the nature of the study, its objectives, and potential risks and benefits, as well as the date informed consent is obtained. The informed consent form will detail the requirements of the volunteer and the fact that he or she is free to withdraw at any time without giving a reason and without prejudice to his or her further medical care.

13.3 Potential Risks and Procedures to Minimize Risk

All potential risks are disclosed to study participants prior to their participation. The potential risks associated with this study include venipuncture and the associated risks. Risks associated with venipuncture include pain, bruising, and infection at the site. Alcohol swabs and proper venipuncture procedure will be followed to minimize the risk of infection.

14 QUALITY ASSURANCE AND QUALITY CONTROL

14.1 Auditing

All material used in clinical studies are subjected to quality control. Quality assurance audits may be performed by the sponsor or any health authority during the course of the study or after its completion.

The Investigator agrees to comply with the sponsor and regulatory requirements in terms of auditing of the study. This includes access to the source documents for source data verification.

14.2 Monitoring

An initiation meeting will be conducted by the sponsor or an approved representative (CRO). At this meeting, the protocol and logistical aspects of the study will be reviewed with the Investigator and all study staff.

Source documents will be reviewed to ensure that all items have been completed and that the data provided are accurate and obtained in the manner specified in the protocol. The participant files will be reviewed to confirm that:

- 1. Informed consent was obtained and documented
- 2. Enrolled participants fulfilled all inclusion criteria and did not meet any exclusion criteria:
- 3. AE/SAE reporting has been performed as applicable
- 4. Study visits have been conducted as per protocol and information has been recorded in the appropriate place in the source document
- 5. The study product is being stored correctly and an accurate record of its dispensation to the study participants is being maintained (accountability)

Incorrect, inappropriate, or illegible entries in the participant files will be returned to the Investigator or designee for correction. No data disclosing the identity of participants will leave the study center. The Investigator and any designees will maintain confidentiality of all participant records.

The Investigator will permit trial-related monitoring, audits, IRB/IEC review, and regulatory inspections and will allow direct access to source data and documents for these purposes.

14.3 Data Management

Data required for the analysis will be acquired from source documentation (including laboratory reports) and entered into OpenClinica Enterprise Version 4 (OC4) study instance designed specifically for this study. The database design starts by revising the finalized study protocol and source documents. eCRFs (electronic case report form) will be created and coded as per study protocol and source documents. The two environments for the database will be created: test instance and production instance. A UAT (User Acceptance Testing) of the database will be performed in the test environment. The database will be reviewed thoroughly to ensure that all datapoints have been completed and that the data collected is accurate and obtained as specified in the study protocol. After conducting this quality control on content, functionality and validation checks, the database will be approved be moved to the production environment. A password protected user ID's will be created which will give access to the limited and trained authorized

personnel. Only properly trained Data management staff will be granted access to perform database designing, according to SOP PC 115 GCP - Designing Database in OpenClinica Enterprise Version and SOP PC 114 GCP - Creating user in OpenClinica Enterprise Version. A study specific Data Management Plan will be generated after the finalization of the database.

The standard data validation and edit checks will be performed on the production environment of the study by designing study specific validation checks and restrictions as per study protocol. Automatic and manually generated discrepancies will be queried and managed according to the SOP PC 116 GCP - Discrepancy Management SOP in OpenClinica Enterprise Version 4. Data will be extracted and tables will be created, queried and exported during and at the end of study using PostgreSQL tool (pgadminIII 9.5) and MS Access.

For Statistical analysis, the validated soft lock copy of the blinded study database will be sent to the Statistician to perform the analysis. The study database will be a read-only file to ascertain changes in the data are not made during or after the analysis.

High safety standards for the transfer and storage of study data are guaranteed by the use of technologies such as password protection, firewalls and periodic backup to protect stored data.

15 APPENDICES

15.1 Appendix I: Schedule of Assessments

Period 1 Period 2

Procedures/assessments	Visit 1 Scree	Visit 2 Day 1 (+1	Visit 3 Day 3 (+1	Visit 4 Day 5 (+1	Visit 5 Day 8 (+1 Day)	Visit 6 Day 1 (+1	Visit 7 Day 3 (+1	Visit 8 Day 5 (+1	Visit 9 Day 8 (+1
	n	Day)	Day)	Day)		Day)	Day)	Day)	Day)
Informed consent	Х								
Review inclusion/exclusion	V	V							
criteria	X	X							
Review medical history	Х								
Review concomitant	Х	Х	Х	Х	Х	Х	Х	Х	Х
therapies	^	^	^	^	^	Α	^	^	^
Vitals: Height*, weight, heart									
rate, blood pressure	X	X	X	X	X	Х	X	X	X
*Height will only be	_ ^	_ ^	_ ^	^	^	^	_ ^	_ ^	^
measured at Visit 1									
Urine pregnancy test	X	X							
Electrocardiogram (EKG)	Х								
Physical examination	X	Х							Х
Randomization		Х							
CBC, electrolytes (Na, K, Cl),									
HbA1c*, fasting glucose,									
eGFR, creatinine, AST, ALT,	X				X	Х			X
and total bilirubin	_ ^					Λ			Λ
*HbA1c will only be									
measured at Visit 1									
Maximum heart rate (HR _{max})	X								
treadmill test									
Skin fluoroscopy for NADH		X			X	Х			Х
analysis (optional)		^							
Blood Collection for NAD+		X	X	X	X	Х	X	X	X
analysis				,					
Blood Collection for									
GSH/GSSG and ATP/AMP		X			X	X			Х
analyses									
OGTT: glucose and insulin T=									
0, 15m, 30m, 45m, 60m,		X			X	X			X
90m, 2h									
Questionnaire		Х	Х	Х	X	Х	X	X	Х

Protocol 19RNHB:

A randomized, double-blind, comparator-controlled, cross-over study to investigate the safety and efficacy of RiaGev $^{\text{\tiny TM}}$ in healthy adults

Procedures/assessments	Visit 1 Scree n	Visit 2 Day 1 (+1 Day)	Visit 3 Day 3 (+1 Day)	Visit 4 Day 5 (+1 Day)	Visit 5 Day 8 (+1 Day)	Visit 6 Day 1 (+1 Day)	Visit 7 Day 3 (+1 Day)	Visit 8 Day 5 (+1 Day)	Visit 9 Day 8 (+1 Day)
Treadmill Exercise protocol		Х			Х	Х			Х
Salivary Collection Kit Dispensed	Х	Х	Х	Х	Х	Х	Х	Х	
Salivary Collection Kit Returned		Х	Х	Х	Х	Х	Х	Х	Х
Food Records Dispensed	Х	Х	Х	Х	Х	Х	Х	Х	
Food Records Collected		Х	Х	Х	Х	Х	Х	Х	Х
IP Dispensed		Х	Х	Х		Х	X	Х	
IP Returned			Х	Х	Х		X	Х	Х
Subject Diary Dispensed	Х	Х	Х	Х	Х	Х	Х	Х	
Subject Diary Returned		Х	Х	Х	Х	Х	Х	Х	Х
Standardized Meal		Х			Х	Х			Х
Compliance Calculated			Х	Х	Х		Х	Х	Х
Adverse Events	X	Х	Х	Х	Х	Х	Х	Х	Х

7-day washout (+3 days)

